9.5. Discontinuation/Withdrawal of Infants

9.5.1. Discontinuation Criteria

Subjects will be discontinued from the study medication after evaluation by the Investigator and Sponsor's Medical Monitor in any of the following cases:

- Any CTCAE Grade 3 or 4 adverse event (see Section 11.3) that the investigator considers related to study medication and not attributable to the underlying disease or considered common events listed in Appendix E.
- · Systemic hypersensitivity reaction related to study medication.
- Non-compliance of the subject's parent(s) or legal guardian(s) with study procedures.
- Other reasons regarded as warranting subject's discontinuation from study medication.
- Premature study termination as described below in this section.

The parent or guardian has the right to withdraw the infant from the trial at any time. In addition, the Investigator may discontinue an infant from the trial at any time if the Investigator considers it necessary for any reason including:

- Non-compliance of the subject's parent(s) or legal guardian(s) with study procedures as evaluated by the Investigator and/or Sponsor as warranting subject's discontinuation from study medication
- An adverse event requiring discontinuation of the trial medication or resulting in inability to continue to comply with trial procedures
- Other reasons regarded by the Investigator as warranting subject's discontinuation from study medication
- · Parental withdrawal of consent
- Major congenital malformation a genetic, metabolic, or endocrine disorder diagnosed after enrolment that is known to be congenital

The reason for withdrawal will be recorded in the source documentation and the eCRF. Parents and guardians, if willing, will be encouraged to return to the site for safety follow-up visits per the study schedule in the event of withdrawal.

If withdrawal of the infant is due to an adverse event, the Investigator will arrange for follow-up visits or telephone calls until the adverse event has resolved or stabilised.

If the event causing the withdrawal occurred within the first 28 days of the study and while consent
is still obtained, the infant will stop consuming the study medication; however, the infant will be
followed up and the data will be recorded for all remaining study visits up to final study visit at 24
months corrected age.

- AEs considered related to the trial medication as judged by a medically qualified investigator and all SAEs (related and unrelated to trial medication) will be followed until resolution. Resolution is defined as the return to baseline status or stabilization of the condition when investigator deems further observations or examinations no longer required as medically indicated.
- If the event causing the withdrawal occurred between days 28 and the final study visit (follow-up visit), and the event was designated as not product-related, the study withdrawal will be recorded with no additional follow up.

9.5.2. Premature Study Termination

The study subjects are expected to experience many adverse events, including severe adverse events related to premature birth, invasive surgery, or other underlying conditions including potential to develop NEC. NEC is characterized by the sudden onset of gastrointestinal distress that may include symptoms such as vomiting, abdominal distention, bloody stools, or dilated loops of bowel that leads to cessation of enteral feedings. Therefore, all safety concerns potentially leading to study termination will be referred to the Data Monitoring Committee (DMC), which is responsible for a formal assessment of the safety of the study. This Board will propose the appropriate course of action to the Sponsor.

Individual Events:

Any of the following individual events would be referred by the study Medical Monitor to the DMC chairman for review, who may decide that the events warrant a full DMC review. The DMC will review these events unblinded to fully evaluate the potential risk to subjects in this trial. Given this is a blinded trial, the DMC review is required to consider if the events, both serious and related non-serious events, are occurring more frequently in the active arms and to judge whether there is a meaningful likelihood that these events are drug-related. The DMC may recommend to the Sponsor to stop the study, or any portion of it, at any time for safety reasons on the basis of their review. Individual events that may trigger a DMC review based on individual cases:

- Two or more cases of Grade 3 or greater allergic reactions or anaphylaxis, that the investigator deems as possibly related to study medication;
- Any case of autoimmune disease associated with neutralizing antibodies to insulin and where other related causes, such as Type I diabetes, are ruled out;
- Two or more cases of persistent Grade 3 or greater hypoglycemia that is non-responsive to treatment within 72-hours and reoccurs after temporary discontinuation of study medication and re-challenged.

Further, the Medical Monitor will be responsible for review of all reported SAEs in an ongoing manner. Any SAE that is deemed potentially related to study medication, or of particular concern by the Medical Monitor, will also be sent to the DMC Chairman for review within 15 days. The DMC Chairman may decide to bring any individual SAE event that may be related and of concern to the full DMC for review.

Collective Events:

The Medical Monitor and DMC will review aggregate safety data in an ongoing manner, at DMC meetings which will be held approximately each 4 months throughout the trial. The Medical Monitor will remain blinded to treatment assignment for cumulative data at all times, but may refer any safety concerns based on review of safety data to the DMC for further evaluation. The DMC will receive unblinded safety data summaries from an independent statistician that is assigned to prepare the unblinded study reports for all subjects at each DMC meeting. The DMC statistician will compare the event rates for AEs between the groups and the probability that the groups differ in the frequency of events. If there are differences in Grade 3 or higher adverse events that differ materially between the active arms and/or placebo, and that may be attributable to study medication based on the mechanism of action of the drug, the DMC has the option to recommend that the Sponsor stop the study, or modify the protocol for safety reasons.

The study may also be prematurely terminated for administrative reasons, ethical considerations, at the request of local regulatory agencies, or for any other reason the Sponsor deems appropriate.

10. INVESTIGATIONAL MEDICINAL PRODUCT (IMP)

10.1. IMP Description

NTRA-2112

The study medications include an active formulation designated NTRA-2112 with human insulin in 2 different doses as the active pharmaceutical ingredient and a placebo formulation. The placebo formulation consists of the same inactive ingredients as NTRA-2112.

NTRA-2112 is incorporated into preterm infant's formula, own mother's milk and pasteurized breast milk (donor breast milk) for enteral administration. NTRA-2112 may also be reconstituted with normal (0.9% NaCl) or half normal saline (0.45% NaCl) for enteral administration, as described in the pharmacy manual. Natural insulin activity level is lost in pasteurized breast milk and absent in formula. The final insulin concentration obtained with NTRA-2112 in the infant's nutrition is physiological and within the range present in human breast milk and colostrum.

		W
s.		
	92	
2		

	-	
	.	
		_

Dosage form:

Powder for oral solution added to own mother's milk, pasteurized breast milk, infant's formula.

10.2. Presentation and Storage Conditions

0.5g powder for oral solution in stick packs. The stick packs should be stored at room temperature in a cool and dry place (further instructions are available in the Pharmacy Manual).

10.3. Method of Administration

The NTRA-2112 and placebo powder will be administered for 28 days or until discharge. The product is provided in 0.5g stick packs.

NTRA-2112 TREATMENT A, 0.04 IU/g to obtain 400 μ U/ml Insulin; NTRA-2112 TREATMENT B, 0.2 IU/g to obtain 2000 μ U/ml insulin; NTRA-2112 mimics the insulin levels in human breast milk and amniotic fluid in-utero. NTRA-2112 may be reconstituted with normal saline as described in the pharmacy manual.

The powder will be administered preferably with all daily enteral feedings, but at least four times each day at enteral feedings according to the study definitions and enteral feeding protocol only (see Appendix A).

10.4. Concomitant Therapy, Restrictions and Rescue Treatment

There are no limitations or restrictions on concomitant therapy.

Rescue medication will be administered according to the Investigator's discretion.

In case of overdose, the glucose level should be monitored carefully for 12 hours and treated according to Investigator's discretion.

10.5. Treatment Compliance

The compliance check will be based on the number of meals to which NTRA-2112 or placebo was added (i.e., actually taken) to the infant's planned daily enteral nutrition. Missed doses should not be replaced or added.

Compliance should be emphasised; however, randomized infants will not be discontinued for lack of compliance.

Full or partial dose interruptions are permitted at the Investigator's discretion; interruptions should last no longer than 3 consecutive days.

10.6. Packaging and Labelling

The IMP (NTRA-2112 and Placebo) is packed in stick packs. Secondary carton packaging is provided with 200 stick packs for each infant, which generally is the sufficient amount of stick packs for the entire treatment period. Each infant will have a designated carton package of study medication. In case of a need, an unscheduled re-supply of additional IMP kit can be assigned to the infant.

All labelling complies with Volume 4. Good Manufacturing Practices, Annex 13. Manufacture of investigational medicinal products, July 2010.

10.7. Storage of Study Medication

Study medication will be stored at room temperature in the pharmacy or in the neonatal intensive care unit, depending on where the institution stores medication and prepared medication for the study infants.

Further instructions are available in the Pharmacy Manual.

10.8. Accountability of the Study Medication

Upon receipt of study drugs, the Investigator (or designee) will conduct an inventory count of the supplies. The Investigator will retain a copy of this inventory at the site and provide a copy to the study monitor. The study monitor may check the inventory of supplies at the study site at any time during the study.

Drug supplies, which the sponsor will provide, must be kept in a secure, limited access storage area under the storage conditions defined by the sponsor (see Pharmacy Manual).

The Investigator, pharmacist and/or investigational drug storage manager will receive the investigational drugs when all country-specific required approvals are in place and all required country-specific essential documents are provided to Nutrinia or its designee.

The Investigator, pharmacist and/or investigational drug storage manager must maintain records of the product's delivery to the trial site, the inventory at the site, the use by each infant, and the return to the Sponsor of unused or partially used product. These records will include dates, quantities, batch/serial numbers, re-test ('use by') dates, and the unique kit numbers assigned to the investigational product and

the trial infants' study number. The Investigator, pharmacist and/or investigational drug storage manager will maintain records that document adequately that the infants were provided the doses specified by the protocol, plus kits assigned by randomization system and reconcile all investigational products received from the Sponsor. At the time of return to the Sponsor, the Investigator, pharmacist and/or investigational drug storage manager must verify that all unused or partially used drug supplies have been returned and that no remaining supplies are in the Investigator's possession.

The study monitor is responsible for ensuring that the Investigator (or designee) has correctly documented the dispensing of study drugs on the dispensing log. The study monitor will perform an inventory of study drugs at routine monitoring visits and at the closeout visit to the site.

11. SAFETY MEASURMENTS

Safety will be evaluated daily during the treatment period. An additional safety evaluation will be performed at discharge or end of treatment and at the final study visit (follow-up visit).

11.2. Causality

The Investigator will determine the relationship of an AE to the study drug and will record it on the source documents and eCRF, using the categories defined below.

Causality Category	Description		
Unlikely	A clinical event, including a laboratory test abnormality, with a temporal relationship to drug administration, that makes a causal relationship improbable, and in which other drugs, chemicals, or the underlying disease provide plausible explanations. For the purpose of this protocol, the term unlikely will be considered not related to study medication and will be termed an "Adverse Event".		
Possible	A clinical event, including a laboratory test abnormality, with a reasonable time sequence to administration of the drug, but that could also be explained by concurrent disease or other drugs or chemicals. Information on drug withdrawal may be lacking or unclear. For the purpose of this protocol, an event that has possible relationship to study medication will be defined as a "Suspected Adverse Drug Reaction".		

Probable	A clinical event, including a laboratory test abnormality, with a reasonable time sequence to administration of the drug, unlikely to be attributed to concurrent disease or other drugs or chemicals, and that follows a clinically reasonable response on withdrawal. For the purpose of this protocol, an event that has probable relationship to study medication will be defined as an "Adverse Drug Reaction".
----------	--

11.3. Collecting, Recording and Reporting of Adverse Events and Serious Adverse Events

Treatment-emergent AEs are events that are not present at screening, or if present at screening, have worsened in severity or frequency.

Data regarding all treatment-emergent AEs will be collected in this study and recorded in the source documentation and in the eCRF, whether or not the event is attributed to trial medication. Pre-treatment emergent events will not be considered as AE and will be recorded as medical history.

Adverse event monitoring will be captured throughout the study from Day 1 (initiation of dosing) until the final study visit (follow-up visit).

AEs and SAEs will be evaluated daily during the treatment period. An additional safety evaluation will be performed at discharge or end of treatment and at final study visit (follow-up visit).

The following information will be recorded: description, date of onset and end date, severity, assessment of relatedness to trial medication, other suspect drug or device, and action taken. Follow-up information should be provided as necessary. The investigator will assess AEs for severity, for relationship to the study drug, and as to whether the event meets one or more of the definitions of an SAE.

AEs will be graded on a 5-point scale (mild, moderate, severe, life-threatening, and death) and reported as indicated in the source documentation and in the eCRF. Severity of such an AE is defined as follows:

Table 2: Severity Assessment Terminology for Reporting Adverse Events

CTCAE Grade	Common Term	Description	
1	Mild	Mild; asymptomatic or mild symptoms; clinical or diagnost observations only; intervention not indicated.	
2	Moderate	Moderate; minimal, local or noninvasive intervention indicated; limiting age-appropriate instrumental Activities of Daily Living (ADL).	
3	Severe	Severe or medically significant but not immediately lifethreatening; hospitalization or prolongation of hospitalization indicated;	
4	Life-threatening	Life-threatening consequences; urgent intervention indicated.	

5	Death	Outcome of AE was death
---	-------	-------------------------

AEs that are not described on the CTCAE v 4.03 will be graded using the scale in Table 2.

In order to classify adverse events and diseases, the sponsor or designee will use the Medical Dictionary for Regulatory Activities (MedDRA) to assign preferred terms to the original terms entered in the eCRF.

AEs considered related to the trial medication as judged by a medically qualified investigator and all SAEs (related and unrelated to trial medication) must be followed until resolution. Resolution is defined as the return to baseline status or stabilization of the condition with the expectation that it will remain chronic.

The Investigator will use clinical judgment to decide whether or not an AE is of sufficient severity to require the study infant's removal from treatment. A participant's parents or legal guardian may also voluntarily withdraw from treatment for what he or she perceives as an intolerable AE. If either of these occurs, the infant must undergo an end of trial assessment and be given appropriate care under medical supervision until symptoms cease, or the condition becomes stable.

All SAEs must be reported to the Sponsor by the Investigator, study coordinator, other designated study personnel, or clinical research associate within 24 hours of notification of the SAE for any related SAEs and any SAE resulted in death (related or unrelated), and within 48 hours for SAEs unrelated to the investigational product, other than death. To report such events, an SAE form must be completed by the Investigator and/or designee and sent by email or fax with relevant information.

The Investigator or designee must provide further information on the SAE as soon as it is available. This should include a copy of the completed SAE form, and any other information that will assist the understanding of the event. Significant new information on ongoing SAEs should be provided promptly as a follow-up.

The Investigator and/or designee also must report all SAEs promptly to the appropriate Independent ethics committee (IEC) / Institutional Review Board (IRB) as required by the institution.

	3		
	V2.		-
			- U
0			
		K	

All SAE information must be recorded in ink on the SAE form provided by the Sponsor and then printed and signed by the Investigator who completed the SAE form. Additional follow-up information (e.g., test results, autopsy, and discharge summary) must be obtained to supplement the SAE report form. A copy of all initial and follow-up reports must be filed with the subject's source documentation.

An SAE reporting flow chart is provided in Appendix C.

[figure not shown]

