2.2.1.4 Sensitivity Analysis: Missing Values

Some infants in the FAS are expected to drop out of the study or, for some other reason, not to have a ranking. As described in Section 2.2.1.3, multiple imputation will be used to include these infants in the analysis of the primary and key secondary endpoint.

The following sensitivity analyses will be conducted on the primary and key secondary endpoint to explore the effect of these missing values:

- Worst reasonable case analysis: Infants in an NTRA-2112 group with a missing rank will be assigned the median rank in the placebo group and infants in the placebo group with a missing rank will be assigned the median rank in the combined NTRA-2112 groups. The van Elteren test, stratified by gestation age group and region (North America, Europe, and Israel) will be performed.
- **Best reasonable case analysis**: Infants in an NTRA-2112 group with a missing rank will be assigned the median rank in the respective NTRA-2112 group and infants in the placebo group with a missing rank will be assigned the median rank in the

Confidential Page 25 of 40

placebo group. The van Elteren test, stratified by gestation age group and region (North America, Europe, and Israel) will be performed.

Tipping point analysis: Infants in either of the NTRA-2112 groups with a missing rank will be assigned varying ranks to find the point at which statistical significance is lost. Specifically, if the outcome of the hypothesis test is in favor of a NTRA-2112 group over the placebo group (P-value <0.05), then one day will be added to each of the imputed values for the NTRA-2112 group in each copy of the imputed dataset, whilst the data for the placebo group will remain the same. The 5 imputed datasets will then be combined to run the van Elteren test results using PROC MI procedure in SAS. This "day shifting" will be repeated with one extra day at a time until the outcome of the hypothesis test is no longer in favor of the NTRA-2112 group over the placebo group (i.e. the P-value becomes greater than 0.05). As the overall ranks of NTRA-2112 group increase as the results of adding one day each time to each imputed missing rank, the highest rank for the imputed missing ranks will be truncated at Day 30 (implying that a missing data point is as bad as a death).

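### Protocol 11.3 and the second list in 9.5.1 can end trial participation for an infant who only stops study drug for an adverse event, contrary to the 9.5.1 follow-up rule, risking avoidable missing outcomes

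*Protocol*

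**What the plan says.** Protocol 11.3 describes two situations, both about stopping drug. In the first, "The Investigator will use clinical judgment to decide whether or not an AE is of sufficient severity to require the study infant's removal from treatment". In the second, a parent or guardian "may also voluntarily withdraw from treatment for what he or she perceives as an intolerable AE". The consequence is the same for both and is mandatory: "If either of these occurs, the infant must undergo an end of trial assessment". Medical care then continues until the event resolves or stabilises. The paragraph does not mention the remaining study visits.

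Protocol 9.5.1 contains three relevant statements:

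- Its first list gives reasons for stopping study medication.
- Its second list gives reasons for which the investigator may discontinue an infant from the trial. One of them is "An adverse event requiring discontinuation of the trial medication or resulting in inability to continue to comply with trial procedures".
- Where the event falls in the first 28 days and consent remains, drug stops but participation goes on, with the infant "followed up and the data will be recorded for all remaining study visits up to final study visit". That visit is the one at 24 months corrected age.

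SAP 1.6.3 sets the end of study at the 24-month corrected-age visit. SAP 1.5.1 labels the full analysis set (FAS) intention-to-treat. SAP 2.2.1.4 anticipates gaps: "Some infants in the FAS are expected to drop out of the study or, for some other reason, not to have a ranking". SAP 1.6.5 sends missing ranks for the primary and key secondary endpoints to multiple imputation.

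**The concern.** One event, an adverse event that stops drug during Days 1 to 28, falls under rules that do not agree. Two places allow a site to treat it as the end of the infant's participation, and one requires follow-up to continue. Sites may resolve this differently.

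If a site closes data collection when drug stops, an infant not yet at full feeding has no NFE. Drug is given only until discharge or Day 28, so the stop comes before discharge, and NRD is missing unless readiness had already been met. NEC or death after closure but before full feeding could also go unrecorded, although the SAP gives those outcomes the worst ranks.

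Infants lost this way are lost because of tolerability. If stops are more common on active drug and the imputed values are more favourable than the true ones, the error favours NTRA-2112.

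**Working it through.** **Text comparison**

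| Place | Trigger | Consequence |
|---|---|---|
| Protocol 11.3 | Removal or withdrawal from treatment for an AE | End-of-trial assessment, then care until resolved or stable |
| Protocol 9.5.1, second list | AE requiring drug discontinuation | Investigator may discontinue the infant from the trial |
| Protocol 9.5.1, first-28-day rule | Event in first 28 days, consent in place | Drug stops; data recorded to 24 months corrected age |
| SAP 1.6.3 | – | End of study is the 24-month visit |

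The first two rows do not fit the last two, so part of the conflict lies inside 9.5.1.

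**Plan's own figure** (SAP 1.3.3: means 8.0 and 6.6 days, SD 3.5, two-sided 5%, 85% power)

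n = 2 × (1.960 + 1.036)² × (3.5/1.4)² = 2 × 8.98 × 6.25 = 112.2, so 113 per group. The exact t-test gives 114 and the SAP states 115, so the figure reproduces. Raising 115 to 130 allows for 1 − 115/130 = 11.5% missing.

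**Power is not the main issue.** By the normal approximation, power at 130 per group is 89.7%. With an assumed 5% or 10% of outcomes lost it is 88.2% or 86.4%.

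**Who could lose NFE.** Using the planned means and SD with a normal approximation, the share not yet at full feeding (active–placebo) is 85–92% at Day 3, 17–28% at Day 10 and 2–4% at Day 14. Early stops put NFE at risk. Later stops mostly put NRD at risk.

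**Possible bias.** The documents give no AE-stop rate, so all rates and true values here are assumptions. Let a and p be the shares lost before full feeding on active and placebo, T the mean true NFE of those infants, and suppose they are imputed from their own arm. On the mean scale:

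overstatement = a × (T − 6.6) − p × (T − 8.0)

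- a = 5%, p = 2%, T = 12: 0.270 − 0.080 = 0.19 days
- a = 5%, p = 2%, T = 16: 0.470 − 0.160 = 0.31 days

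The SAP estimates the effect by Hodges-Lehmann, which is less sensitive to a few long times. It was simulated with 2,000 replicates, 130 per arm, normal NFE in unrounded days, no stratification, and lost infants' true NFE with mean T and SD 4.

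| Lost, active / placebo | Mean difference, T = 12 to 16 | Hodges-Lehmann, T = 12 to 16 |
|---|---|---|
| 3% / 1% | 0.12–0.20 days | 0.10–0.12 days |
| 5% / 2% | 0.19–0.31 days | 0.16–0.19 days |
| 8% / 3% | 0.31–0.51 days | 0.25–0.32 days |

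Repeat runs vary by one or two hundredths of a day. At 5%/2% the Hodges-Lehmann overstatement is 0.16/1.4 = 11% to 0.19/1.4 = 14% of the planned effect.

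**Dependence on imbalance.** With equal loss m in both arms the formula reduces to m × (8.0 − 6.6) = 1.4m, which is 0.07 days at 5%. Most of the bias comes from unequal stopping.

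**The case against.** Section 11.3 is an AE-reporting section. It requires an assessment and care; it does not say that the infant leaves the trial or that recording stops. The same section says AE capture runs to the final study visit. Section 9.5.1, the section on discontinuation, is explicit about follow-up, and a site could satisfy both. The visit may also be defined in Protocol 9.1 to 9.4 or in Table 1, which are not in the available text, so a missing definition cannot be held against the plan. All this stands, and it limits the point to what sites could do. The mandatory wording and the trial-discontinuation entry in 9.5.1 still conflict with the follow-up rule.

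Safeguards exist. NEC and death before full feeding are ranked when recorded. SAP 2.2.1.4 has a worst-reasonable-case analysis and a tipping-point analysis that adds days to imputed active-arm values only, up to Day 30, which is the direction of concern. These limit and can expose the bias. However, the worst-reasonable case assigns only the placebo median rank, the log-rank analysis censors early withdrawals at last participation, and the tipping-point analysis is supportive. None replaces observed data.

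These infants would usually still be inpatients, so with consent much of the information could be recovered from hospital records. That weakens any claim of permanent loss, and also means that collecting the data prospectively costs little.

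**Conclusion.** The conflict is real and should be reconciled. Its consequence is a risk of avoidable, tolerability-related missing NFE (if full feeding has not been reached) and NRD (if the infant is not yet discharged or ready), together with possible missed NEC or death.

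A reader might infer that sites following 11.3 necessarily lose both outcomes in every infant who does not tolerate treatment. The documents do not support that: 11.3 never orders data collection to stop, infants already at full feeding keep NFE, and those already ready for discharge keep NRD.

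A reader might also take the mean-scale figures as the bias in the trial's result, or assume that lost infants will receive values typical of those who tolerated the drug. Neither is established. The planned estimator is Hodges-Lehmann, and the imputation text (SAP 2.2.1.3.1) is not available.

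The illustrative 0.16 to 0.19 days requires own-arm imputation, early closure for every counted infant, every such stop preceding full feeding, stops 2.5 times as frequent on active drug (5% against 2%), and true NFE averaging 12 to 16 days. The actual size is unknown.

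**What to change.** Reconcile Protocol 9.5.1 and 11.3 without changing any clinical stopping rule:

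1. In 11.3, call the visit an end-of-treatment assessment and cross-refer to the follow-up rule in 9.5.1.
2. In the second list of 9.5.1, separate reasons for stopping medication from withdrawal from the trial.
3. State that daily enteral volume, NEC, death, and discharge or readiness data continue to be recorded after an AE-driven treatment stop, unless consent to data collection is withdrawn. The recording should run to Day 28 for NFE and to Day 180 for NRD, matching the SAP's observation periods.

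The cost is a few sentences in a protocol amendment and a note to sites. The infants are generally still in hospital with these data being charted, so little extra collection is needed.
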